6.3.5.3 Day 8 (+/-1), Cycle 1 (Cohorts 7, 8, 9)

On Day 8 of Cycle 1, the procedures listed below will be performed.

- continuous infusion via a central venous catheter of TK216 study drug;
- clinical laboratory tests (hematology, clinical chemistries, coagulation, urinalysis);
- a single pharmacokinetic sample (see section 6.3.9);
-
- vital signs;
- symptom-driven physical examination;
- concomitant medication assessment;
- adverse event assessment.

6.3.5.4 Day 11 (+/-1), All Schedule Escalation Cohorts and Cycles (Cohorts 7, 8, 9)

On Day 11, the procedures listed below will be performed, as applicable to patients continuing the infusion or patients ending the scheduled infusion.

- continuous infusion via a central venous catheter of study drug, if applicable;
- a single pharmacokinetic sample, if the scheduled infusion is continuing (see section 6.3.9), or;
- pharmacokinetic samples, in Cycle 1 only, if the scheduled infusion is ending (see section 6.3.9);
- for Cycle 1 only, pharmacodynamic sample, if ending the scheduled infusion;
- clinical laboratory tests (hematology, clinical chemistries, coagulation, urinalysis), if ending the scheduled infusion;
- vital signs, if ending the scheduled infusion;
- 12-lead ECG, if ending the scheduled infusion;
- symptom-driven physical examination;
- concomitant medication assessment, if ending the scheduled infusion;
- adverse event assessment, if ending the scheduled infusion;

- tumor/disease evaluation soon after stopping scheduled infusion and prior to beginning next infusion, if applicable.

6.3.5.5 Day 15 (+/-1), All Schedule Escalation Cohorts and Cycles (Cohorts 7, 8, 9)

On Day 15, the procedures listed below will be performed, as applicable to patients continuing the infusion or patients ending the scheduled infusion.

- continuous infusion via a central venous catheter of study drug, if applicable;
- clinical laboratory tests (hematology, clinical chemistries, coagulation, urinalysis);
- a single pharmacokinetic sample, if the scheduled infusion is continuing or the patient is in the expansion cohort (see section 6.3.9), or;
- pharmacokinetic samples, in Cycle 1 only, if the scheduled infusion is ending (see section 6.3.9);
- for Cycle 1 only, pharmacodynamic sample, if ending the scheduled infusion;
- vital signs;
- 12-lead ECG, if ending the scheduled infusion;
- symptom-driven physical examination;
- concomitant medication assessment;
- adverse event assessment;
- tumor/disease evaluation soon after stopping scheduled infusion and prior to beginning next infusion, if applicable.

6.3.5.6 Day 18 (+/-1), All Schedule Escalation Cohorts and Cycles (Cohorts 7, 8, 9)

On Day 18, the procedures listed below will be performed, as applicable to patients continuing the infusion or patients ending the scheduled infusion.

- continuous infusion via a central venous catheter of study drug, if applicable;
- clinical laboratory tests (hematology, clinical chemistries, coagulation, urinalysis), if ending the scheduled infusion;
- for cycle 1 only, pharmacodynamic sample, if ending the scheduled infusion;
- a single pharmacokinetic sample, if the scheduled infusion is continuing (see section 6.3.9), or;
- pharmacokinetic samples, during Cycle 1 only, if the scheduled infusion is ending (see section 6.3.9);
- vital signs, if ending the scheduled infusion;
- 12-lead ECG, if ending the scheduled infusion;
- symptom-driven physical examination;
- concomitant medication assessment, if ending the scheduled infusion;
- adverse event assessment, if ending the scheduled infusion;
- tumor/disease evaluation soon after stopping scheduled infusion and prior to beginning next infusion, if applicable.

6.3.5.7 Day 22 (+/-1), All Schedule Escalation Cohorts and Cycles (Cohorts 7, 8, 9)

On Day 22 the procedures listed below will be performed, as applicable to patients continuing the infusion or patients ending the scheduled infusion.

- clinical laboratory tests (hematology, clinical chemistries, coagulation, urinalysis);
- for Cycle 1 only, pharmacodynamic sample;
- pharmacokinetic sample(s) (see section 6.3.9);
- vital signs;
- 12-lead ECG;
- symptom-driven physical examination;
- concomitant medication assessment;
- adverse event assessment;
- tumor/disease evaluation soon after stopping scheduled infusion and prior to beginning next infusion, if applicable.

6.3.5.8 Rest Period, All Schedule Escalation Cohorts, Cycle 1 and Subsequent Cycles (if applicable), Seven Days after ending Infusion (Cohorts 7, 8, 9)

- Cycle 1 of every schedule escalation cohort will have a 14-day rest period. Subsequent cohorts will have a rest period of varying duration (see section 4.3). Seven days (+/- 2 days) after the TK216 infusion is stopped in Cycle 1 (or subsequent cycles, if applicable), the procedures listed below will be performed. The clinical laboratory testing may be done at a local laboratory, and the interview may be conducted by telephone. If a patient is starting a new cycle before this visit (see sections 4.3 and 6.3.8.1), the day 1 clinical laboratory tests should only be repeated if they were not done within 72 hours of starting the infusion.
- clinical laboratory tests (hematology, clinical chemistries, coagulation);
- concomitant medication assessment;
- adverse event assessment.
- This visit may also be considered Day 1 of Cycle 2, or subsequent cycles, if the patient meets the criteria to resume (see Sections 4.3 and 6.3.8.1) at the end of Cycle 1.

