2.4 Part 3 Expansion Cohort

The expansion cohort segment of this study will consist of approximately 18 ES patients.

All patients in the expansion cohort will receive the RP2D of TK216 in conjunction with primary supportive care prophylaxis (e.g., with growth factors, antidiarrheals, antiemetics) for bone marrow and/or gastrointestinal toxicities. The first three patients will also receive vincristine intravenously on the first day of each treatment cycle, at a dose of 0.75 mg/m². If DLT (Table 2) is observed in 1 of 3 patients, an additional three patients will receive the same doses of TK216 and vincristine. If fewer than 1 of 6 patients experience DLT, then the remaining patients in the expansion cohort will receive the RP2D of TK216 plus vincristine given intravenously on the first day of each treatment cycle, at a dose of 1.5 mg/m² to a maximum of 2 mg/m² per dose. If DLT is observed in ≥2 of the first six

patients, then the dosing of vincristine and/or TK216 will be revised in consultation between the Investigators and the Sponsor.

If TK216 treatment has been well tolerated in Cycle 1 and 2, starting in Cycle 3 the duration of the TK216 infusion may be increased (e.g., from 14 to 17 or 14 to 24 days). If the longer infusion is well tolerated, the duration of the TK216 infusion may be increased further in subsequent cycles. There is no maximum treatment duration. If a longer infusion time is not well tolerated, the patient may remain on study, but receive a shorter duration of TK216 infusion in the next treatment cycle. The assessments noted for Days 8+/-1 and 15+/-1 in the Section 16.3 Schedule of Events (Schedule Escalation and Expansion Cohorts) should be performed every 7-8 days during longer infusions (Adverse events, Concomitant medications, Vital signs, Symptom driven physical exam, Hematology, Clinical chemistry, Coagulation, Urinalysis, and Plasma for PK assessment). A complete blood count (CBC with differential) should be obtained approximately half way between the weekly assessment at the study center or local laboratory.

In Part 3 dosing will follow the schedule for the RP2D selected. If TK216 treatment has been well tolerated in Cycles 1 and 2, starting in Cycle 3 the duration of the TK216 infusion may be increased, in consultation with the Sponsor.

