6.3.5 All Schedule Escalation Cohorts and Cycles (Cohorts 7, 8, 9)

No hospitalization is required for the schedule escalation cohorts.

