6.3.5.1 Day 1, All Schedule Escalation Cohorts and Cycles (Cohorts 7, 8, 9)

On Day 1 of Cycle 1 for all schedule escalation cohorts, the following procedures will be performed.

- ECOG or Karnofsky/Lansky performance status**;
- Weight**; height Cycle 1 only
- vital signs;
- 12-lead ECG: pre-dose**; For Cycle 1 only, post-dose between 1 and 3 hours after initiation of infusion;
- clinical laboratory tests (hematology, clinical chemistries, coagulation, urinalysis)**;
- for Cycle 1 only, urine pregnancy test (women of childbearing potential only)**;
- complete physical examination**;
- for Cycles 1 and 2 only, pharmacodynamic samples: pre-dose on Day 1; Samples in subsequent cycles may be collected if clinically indicated, for example, to evaluate biomarkers of response
- a single pharmacokinetic sample (see section 6.3.9);
- a single sample for pharmacogenomics to assess CYP polymorphisms
- the TK216 infusion via a central venous catheter will be initiated; infusion will continue for the number of days assigned in the cohort;
- the vincristine infusion will be administered prior to the start of the TK216 infusion starting in cycle 3+ of schedule escalation cohorts, if applicable;
- the vincristine infusion will be administered prior to the start of the TK216 infusion starting in cycle 1 of expansion cohort, if applicable;

- concomitant medication assessment;
- adverse event assessment.

** If the assessments for ECOG or Karnofsky/Lansky performance status, weight, physical examination, ECG, clinical laboratory tests and urine pregnancy test were performed within approximately 72 hours prior to starting a new infusion cycle, these assessments do not need to be repeated.

6.3.5.2 Day 4 (+/-1), All Schedule Escalation Cohorts and Cycles (Cohorts 7, 8, 9)

On Day 4 of Cycle 1, the procedures listed below will be performed.

- continuous infusion via a central venous catheter of study drug;
- For Cycle 1 only, pharmacodynamic sample;
- a single pharmacokinetic sample (see section 6.3.9) if the patient is in the schedule escalation segment;

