6.3.5.9 Pharmacokinetic Assessments, Schedule Escalation Cohorts, Cycle 1 (Cohorts 7, 8, 9)

During Cycle 1 only of the schedule escalation cohorts, PK assessments will be collected at the end of the cycle infusion, +/- 10 minutes, at the following time points:

- 1 hour prior to stopping the infusion;
- immediately prior to stopping the infusion;
- .5 hours (30 minutes) after stopping the infusion;
- 1 hour after stopping the infusion;
- 2 hours after stopping the infusion;
- 4 hours after stopping the infusion;

- and 8 hours after stopping the infusion.

For all cycles during the schedule escalation and expansion cohorts, a single PK assessment will be done at each of the following days, if the scheduled infusion is continuing: Days (+/- 1) 4, 8, 11, 15, 18, and 22.

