6.3.6 Expansion Cohort (Cohort 10)

4.2.3.1 Expansion Cohort: On study Schedule (Cohort 10)

Patients enrolled in the Expansion Cohort will be assessed and treated the same as described for the Schedule Escalation Cohorts in Section 6.3.5, as applicable to the selected regimen.

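### Section 6.3.5.3 confines the Day 8 visit to Cycle 1, so from Cycle 2 an unlengthened 10- or 14-day infusion in Parts 2 and 3 has no listed mid-infusion blood count

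*Combined protocol and SAP*

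**What the plan says.** Section 6.3.5 covers all schedule escalation cohorts and all their cycles, and adds: "No hospitalization is required for the schedule escalation cohorts". Its visits for Days 1, 4, 11, 15, 18 and 22 carry the same all-cycle scope in their headings. Day 8 (6.3.5.3) is the exception. Its heading names Cycle 1, and so does its opening sentence: "On Day 8 of Cycle 1, the procedures listed below will be performed".

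Section 6.3.5.9 sets a different scope for PK: "For all cycles during the schedule escalation and expansion cohorts, a single PK assessment will be done at each of the following days". Day 8 is among those days, provided the infusion is still running.

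Hematology and chemistry are listed as follows. Day 1 has them. Day 4 has none. Day 8 has them, within the Cycle 1 limit. Day 11 has "clinical laboratory tests (hematology, clinical chemistries, coagulation, urinalysis), if ending the scheduled infusion". Days 15 and 22 have them without condition.

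Section 6.3.6 carries this into Part 3: expansion patients "will be assessed and treated the same as described for the Schedule Escalation Cohorts in Section 6.3.5", as far as the chosen regimen allows. Section 2.4 adds: "In Part 3 dosing will follow the schedule for the RP2D selected".

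**The concern.** A site that follows 6.3.5.3 holds no Day 8 visit after Cycle 1. A site that follows the parent heading, or 6.3.5.9, does. Both cannot be right.

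The difference is one of safety monitoring. The suggested holds in 2.6.1.1 for Grade 4 neutropenia and thrombocytopenia depend on blood counts, and so does the use of growth factor for neutropenia that the same section permits after the first cycle. Without Day 8, the first listed count after Day 1 comes at about the end of a 10- or 14-day infusion, too late to prompt a hold during it.

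The cycles affected are those in which exposure can rise. In Part 2 the daily dose may go up from Cycle 2 after a well-tolerated cycle. Vincristine may start from Cycle 3 at 0.75 mg/m² and move to 1.5 mg/m² in the next cycle. The rest period may also be shortened after Cycle 1. These patients need not be in hospital, and Cohorts 7 to 10 may enroll from age 10.

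**Working it through.** The plan states no figure for this interval, so there is none to reproduce. The check is a count of listed panels (hematology and chemistry) through each infusion.

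**Inputs**
- Panel days in Parts 2 and 3: 6.3.5.1 to 6.3.5.5, as set out above. Day 11 counts only when the infusion ends then, which is the 10-day schedule. Day 15 is the end-of-infusion visit of the 14-day schedule.
- Infusion lengths: 10 days for the first schedule cohort and 14 days for the illustrated second one (2.3). Fourteen days is also the example base length in 2.4.
- Part 4 panel days: 4.2.4.1 to 4.2.4.5, under a parent heading for all cycles.
- Visit window: ±1 day from Day 4 onward. Day 1 tests may be taken up to about 72 hours (3 days) before the infusion starts.

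**Formulas**
- Gap = later panel day − earlier panel day.
- Mid-infusion panels = listed panel days strictly between Day 1 and the end-of-infusion visit.

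| Infusion | Cycle | Panel days to end of infusion | Gaps (days) | Mid-infusion panels |
|---|---|---|---|---|
| 14-day | 1 | 1, 8, 15 | 7, 7 | 1 |
| 14-day | 2 onward | 1, 15 | 14 | 0 |
| 10-day | 1 | 1, 8, 11 | 7, 3 | 1 |
| 10-day | 2 onward | 1, 11 | 10 | 0 |
| Part 4, 28-day | all | 1, 8, 15, 21, 28 | 7, 7, 6, 7 | 3 |

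**First panel after Day 1, with the ±1 day window**
- Day 8 held: Days 7 to 9, so 7 − 1 = 6 to 9 − 1 = 8 days after Day 1.
- 10-day infusion, no Day 8: Days 10 to 12, so 9 to 11 days.
- 14-day infusion, no Day 8: Days 14 to 16, so 13 to 15 days.
- If the Day 1 tests were drawn 3 days early, the longest interval for the 14-day infusion is 15 + 3 = 18 days.

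**Does other text fill the gap?**
- Section 4.1.5 requires laboratory review before dosing on Day 1 of each cycle, and the restart criteria in 2.3 also apply on Day 1. Neither reaches mid-infusion.
- Sections 2.3 and 2.4 ask for assessments every 7 to 8 days, with an interim blood count, during longer infusions. In both places this follows directly on the provision to lengthen the infusion from Cycle 3, with 14 days as the length being extended. It does not clearly cover a 14-day infusion left at 14 days. Read narrowly, a 17-day infusion gets weekly panels plus interim counts, while a 14-day infusion gets nothing until its end.

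**Is the Cycle 1 wording only loose drafting?** The Day 4 section opens "On Day 4 of Cycle 1, the procedures listed below will be performed" under an all-cycle heading, and the Day 1 section does the same. But both lists mark single items as Cycle 1 only, and Day 1 mentions Cycle 3 onward, so their all-cycle scope can be seen from the contents. The Day 8 list has no such sign, and its heading is restricted too.

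**The case against.** The strongest counter-argument is the Section 16.3 table. Sections 2.3 and 2.4 cite it as holding Day 8 and Day 15 assessments that include hematology and chemistry, and they treat the two days alike as the pattern to repeat when infusions are lengthened from Cycle 3. That suggests Day 8 was meant to continue after Cycle 1. It shows that 16.3 has a Day 8 entry, but not for which cycles, and the table is not in the text reviewed.

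Second, Cycle 1 labels in this section are unreliable. The heading of 6.3.5.9 also ends in Cycle 1, although its body sets the all-cycle PK rule. This supports a drafting slip as the cause. It does not tell a site which instruction to follow.

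Third, longer infusions could mean anything beyond the seven days of Part 1, since 2.3 introduces Part 2 in such terms. The adjacent sentences favor the narrower meaning, and a safety panel should not depend on the choice.

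Fourth, the safeguards that remain are real: Day 1 count thresholds, panels on Days 15 and 22 and in the rest period, a symptom-driven examination on Day 11, adverse event questioning at each visit, and the investigator's freedom to draw extra counts. The holds are only suggested, and Part 3 gives supportive prophylaxis. These reduce the consequence, but none of them requires a count during the infusion.

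Fifth, three panels in Part 4 against none here compares a 28-day infusion with shorter ones. That is fair; the gap in days (7 against 10 or 14) is the better comparison.

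**Conclusion.** The concern holds. Section 6.3.5.3 conflicts with its parent heading, with the other visit-day headings and with the Day 8 PK rule in 6.3.5.9. Followed as listed, mid-infusion panels fall from one in Cycle 1 to none from Cycle 2. The longest nominal gap during infusion goes from 7 to 14 days on the 14-day schedule and from 7 to 10 on the 10-day schedule.

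This rests on three conditions: the visit lists are followed literally, the infusion has not been lengthened, and, for Part 3, the RP2D is a 10- or 14-day schedule. If Section 16.3 lists Day 8 for all cycles, the fault is one of wording only. Cycle 1 DLT assessment is unaffected. The documents give neither event rates nor the timing of count nadirs, so the harm cannot be sized.

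**What to change.** Give 6.3.5.3 the same all-cohorts-and-cycles heading as its neighbors, keeping the ±1 day window and Cohorts 7, 8 and 9. Delete *of Cycle 1* from its first sentence, and make Section 16.3 agree. Through 6.3.6 the change reaches Cohort 10 as well.

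From Cycle 2, panels on a 14-day infusion would then fall on Days 1, 8 and 15, with nominal gaps of 7 and 7 days. The longest Day 8 to Day 15 interval within the windows would be 16 − 7 = 9 days.

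The cost is one heading, one phrase and a check of one table. In the clinic it is one routine panel with vital signs per later cycle, on a day when 6.3.5.9 already calls for a blood draw. The edit is right whatever 16.3 says: it either aligns the text with the table or restores a missing safety count.

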6.3.5.9 Pharmacokinetic Assessments, Schedule Escalation Cohorts, Cycle 1 (Cohorts 7, 8, 9)

During Cycle 1 only of the schedule escalation cohorts, PK assessments will be collected at the end of the cycle infusion, +/- 10 minutes, at the following time points:

- 1 hour prior to stopping the infusion;
- immediately prior to stopping the infusion;
- .5 hours (30 minutes) after stopping the infusion;
- 1 hour after stopping the infusion;
- 2 hours after stopping the infusion;
- 4 hours after stopping the infusion;

- and 8 hours after stopping the infusion.

For all cycles during the schedule escalation and expansion cohorts, a single PK assessment will be done at each of the following days, if the scheduled infusion is continuing: Days (+/- 1) 4, 8, 11, 15, 18, and 22.

6.3.6 Expansion Cohort (Cohort 10)

4.2.3.1 Expansion Cohort: On study Schedule (Cohort 10)

Patients enrolled in the Expansion Cohort will be assessed and treated the same as described for the Schedule Escalation Cohorts in Section 6.3.5, as applicable to the selected regimen.

4.2.3.2 Early Termination/End of Treatment Visit, All Cohorts, All Cycles (Cohort 10)

The following procedures will be performed at the time a patient is discontinued from the study, if prior to completing a cycle. This visit should be performed within 2 days of discontinuation. The End of Treatment Visit will be done if a patient completes a cycle but does not continue to the next cycle. This visit should be performed either at the last visit in the cycle (Day 22) or within 7 days after the completion of the cycle. During the schedule escalation segment, this visit should be done within 2 days if the patient discontinues before the end of cycle 1 or if the patient discontinues during an infusion of any subsequent cycle, or within 7 days if the patient discontinues after the end of an infusion but prior to starting the next cycle.

- ECOG or Karnofsky/Lansky performance status
- vital signs;
- weight;
- complete physical examination;
- 12-lead ECG;
- clinical laboratory tests (hematology, clinical chemistries, coagulation, urinalysis);
- urine pregnancy test: women of child-bearing potential only;
- if a CT scan or MRI is due, it should be done at this visit. The same method of assessing disease must be used throughout the study;
- concomitant medication check;
- adverse event assessment.

4.2.4 Infusion Period, All Cycles (Cohort 11)

As of Protocol version 7.0, the regimen given is to be TK216 175 mg/m² continuous infusion IV for 28 days. The patient will be assessed for toxicities during the 28-day cycles and may take treatment rests, if needed. Treatment rests unrelated to toxicities are not encouraged but may occur at the PI's discretion after discussion with the Sponsor.

4.2.4.1 Day 1 (Cohort 11)

- ECOG or Karnofsky/Lansky performance status**;
- Vital signs and weight**;
- Symptom driven physical examination**;

- Clinical laboratory tests (hematology, clinical chemistries, coagulation, urinalysis)**;
 - Woman of childbearing potential should have a pregnancy test.
- **Cycles 1 and 2 only:** Collect single pre-infusion PK blood sample.
- **Cycles 1 and 2 only:** Collect pre-infusion Pharmacodynamic samples: Biomarkers & PBMC.
- Collect Pharmacogenomic sample: Cycle 1 only
- TK216 infusion via a central venous catheter will be initiated; infusion will continue for 28 days
- Adverse event & concomitant medication assessment.

Additional cycles of therapy may be administered provided that the patient meets the following criteria on Day 1 of each subsequent cycle:

- ANC $\geq 1,000/\text{mm}^3$
- Hemoglobin ≥ 8.0 gm/dL (Blood transfusions are permitted)
- Platelets $\geq 50,000/\text{mm}^3$
- Non-hematologic toxicity recovered to \leq Grade 1 (or tolerable Grade 2)

** If the assessments for ECOG performance status, weight, physical examination, clinical laboratory tests and urine pregnancy test were performed within approximately 72 hours prior to starting a new infusion cycle, these assessments do not need to be repeated. Periodic height check, as determined by the Investigator may be included in the procedures of any cycle.

4.2.4.2 Day 8 (± 1) (Cohort 11)

The procedures listed below will be performed:

- Bag change for TK216
- Vital signs
- Symptom-driven physical examination
- Clinical laboratory tests (hematology, clinical chemistries)
- **Cycles 1 and 2:** Collect single blood samples from a peripheral vein for PK analysis
- Adverse events and concomitant medication assessment

